5.4.2 Adverse Events Requiring Expedited Reporting

All SAEs will be carefully monitored throughout the course of the study.

All SAEs, regardless of relationship to study drug, must be reported by the Investigator to XOMA or its designee within 24 hours of being notified of the event. The Investigator should contact XOMA or its designee by telephone, followed by a faxed initial SAE form. Additional written follow-up information, including a full description of the event and any sequelae, must follow as soon as available.

Telephone Report:

[name].	Office:	[contact]
Medical Monitor		[contact]

Concurrent SAE Form:

[name]	[contact]
	[contact]

For initial SAE reports, record all case details that can be gathered within 24 hours on the SAE Form. The completed SAE form should be faxed immediately upon completion. Relevant follow-up information should be submitted as soon as possible. All SAEs should also be reported to the IRB within the time frame determined by the institution at which the investigation is being carried out.

5.4.3 Special Reporting Situations

Fatal or life-threatening events thought to be caused by study drug should be immediately reported to the Medical Monitor by [contact] Death

Death is an outcome of an event. The **event** that resulted in the death should be recorded and reported on the AE CRF, SAE Form, and Death Report Form.

5.4.3.2 Hospitalizations for Surgical or Diagnostic Procedures

The **illness** leading to the surgical or diagnostic procedure should be recorded as the SAE, not the procedure itself. The procedure should be captured in the case narrative as part of the action taken in response to the illness.

5.5 Type and Duration of Follow-up After Adverse Events

5.5.1 Post Treatment Follow-up

All subjects receiving any amount of drug will be followed until Day 100. All protocoldefined AEs occurring during the treatment and post-treatment periods should be fully evaluated by the Investigator, recorded on the appropriate pages of the CRF, and documented in the subjects' files.

SAEs that occur after the subject has completed the clinical trial generally need not to be reported unless the Investigator believes the event may be related to the administration of study drug.

5.5.2 Post Adverse Event Follow-up

All subjects that experience AEs should be followed until the event resolves or until the subject's participation in the study ends. For those AEs judged by the Investigator to be unrelated to study drug, the outcome at last observation should be recorded in the appropriate pages of the CRF.

Subjects experiencing AEs that were judged by the Investigator to be possibly, probably or definitely related to study drug should be followed until the events resolve or until the Investigator judges the event to be "chronic" or "stable." Resolution of such events are to be documented on the appropriate CRF pages.

6.0 DATA ANALYSIS AND STATISTICAL METHODS

Data will be analyzed for safety, pharmacokinetics, and biological endpoints. Safety analyses will include all subjects who received any amount of study drug. Analyses of the population of subjects who completed treatment may also be performed. Since the sample size is small, no formal statistical testing will be performed. Study results will be summarized by descriptive statistics and to generate by preliminary hypotheses by making comparisons to other patient cohorts when similar measures were made in patients with similar transplant-related characteristics.

6.1 Disposition of the Study Subjects and Conduct of the Study

The disposition of subjects will be described with summaries by dose group of the number of subjects enrolled, the number of subjects treated, and the number of subjects for whom study drug was permanently discontinued (including the reasons).

6.2 Determination of Sample Size

The sample size for this study is based primarily on PK/PD considerations. The planned accrual is six subjects in each of the five successive dose groups. Formal sample size calculations were not done but past experience with this type of study suggests that this number of subjects will be adequate to characterize the PK/PD profile at each dose level.

6.3 Analysis of Treatment Group Comparability

Demographic (age, sex, etc.) and baseline characteristics (pre-treatment variables and conditioning regimens) will be summarized by dose group.

6.4 Biological and Clinical Activity Analysis

The median time to engraftment will be compared by dose group. The mean of inflammatory markers (e.g., LPS and LBP) and opebacan plasma levels will be summarized by assessment time point and dose group. Subjects with inflammatory states such as presence of fever and infection will be summarized and correlated with level of inflammatory markers such as LPS and LBP by dose group. Transplant-related complications will be described for individual subjects experiencing such events and summarized, if sufficient cases warrant such summarization (see Section 3.8.1).

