3.0 STUDY DESIGN

3.1 Description of the Study

This is a phase I/II, open-label, dose- and duration-escalation study of the safety and PK of opebacan in subjects undergoing non-T cell depleted myeloablative HSCT from an allogeneic donor. Subjects who sign an informed consent and pass initial screening prior to the start of their HSCT conditioning regimen will be re-evaluated on Day -1. Subjects who meet the eligibility criteria for HSCT at final screening will begin their IV infusions of opebacan on Day -1. Subjects whose conditioning regimen consists of chemotherapy only will receive a continuous opebacan infusion following completion of chemotherapy treatment on Day -1. Subjects whose conditioning regimen includes total body irradiation (TBI) will have three 1-hour interruptions in their opebacan infusions (one on Day -1 and two on Day 0) to accommodate TBI treatment. Following the final interruption on Day 0, the infusion must be restarted at least 2 hours prior to the HSCT.

The HSCT procedure will take place on Day 0, between 18 and 36 hours following the start of opebacan treatment, and approximately 4 to 12 days following initiation of the conditioning regimen.

Eligible subjects will be assigned to one of five successive dose groups of six subjects each. Subjects in successive dose groups will be treated with opebacan at escalating doses and durations as shown in Table 1.

[figure not shown]
Table 1
Study BPSC030 Dose Groups

[figure not shown]
Dose Group	No. of Subjects	Dose Regimen	Total Dose
1	6	4 mg/kg continuous IV infusion for 30 minutes followed immediately by 6 mg/kg/day continuous IV infusion for 3 days	22 mg/kg
2	6	4 mg/kg continuous IV infusion for 30 minutes followed immediately by 9 mg/kg/day continuous IV infusion for 3 days	31 mg/kg
3	6	4 mg/kg continuous IV infusion for 30 minutes followed immediately by 12 mg/kg/day continuous IV infusion for 3 days	40 mg/kg
4	6	4 mg/kg continuous IV infusion for 30 minutes followed immediately by 12 mg/kg/day continuous IV infusion for 7 days	88 mg/kg
5	6	4 mg/kg continuous IV infusion for 30 minutes followed immediately by 12 mg/kg/day continuous IV infusion for 14 days	172 mg/kg

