For example, attempts at XOMA to model appropriate doses of opebacan to neutralize endotoxin based on *in vitro* and *in vivo* studies have resulted in estimated opebacan blood levels as high as 10 µg/mL—a level which, although safe when given in short infusions, is both clinically impractical and poses possible safety issues if given continuously over extended time periods. On the other hand, evidence of clinical activity, including significant and trending prospective measures of clinical benefit, were observed in a randomized, double-blinded trial in pediatric meningococcemia with 2 mg/kg opebacan administered continuously over 24 hours, yielding steady-state plasma levels of 67 ng/mL.

These mixed results suggest that establishing a dosing rationale for opebacan that seeks efficacy signals while maximizing safety will require the use of a composite of quantitative safety observations from animal toxicology studies, other animal data, and human experience and empirical observations in this population.

3.2.1.2 An Endotoxin Antagonist in an aGvHD Animal Model: Clinical Study Considerations

[figure not shown]
Cooke and colleagues evaluated an endotoxin antagonist (a synthetic lipid-A analogue) in a mouse aGvHD model (Cooke et al., 2001). Results from this study demonstrated that a course of endotoxin antagonist given for six days significantly reduced the later onset of aGvHD. In this animal model, the drug did not need to be present at the time when aGvHD was expected to occur, but rather before onset of aGvHD in a prophylactic mode. If opebacan prophylaxis proves useful in humans receiving stem cell transplants, the duration of such prophylaxis will need to be empirically determined since onset of aGvHD in humans starts between post-transplant Days 21 and 42, later than reported in the mouse model.

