3.3.4 Dose Escalation Plan

Subjects will be enrolled sequentially according to the dose escalation diagram shown in Figure 4. If a DLT occurs in any subject, it must be treated, if necessary, and monitored until it stabilizes or recovers to no worse than CTC grade 2 toxicity (grade 1 if reported toxicity is initially grade 2) prior to additional enrollment. Subjects will be monitored for toxicity with assessments listed in Appendix 1 (Schedule of Assessments).

To minimize the chance of simultaneous graft failures possibly due to exposure to opebacan, only two subjects may be simultaneously enrolled in any dose group until one of them successfully engrafts, defined as ANC $\geq 500/\mu L$ for three consecutive days, with the first day (the day of engraftment) occurring no later than Day 28. Once engraftment occurs in one of the first two subjects in a dose group, the third subject may be enrolled. When engraftment occurs in a second subject within a dose group, the fourth subject may be enrolled, and when

engraftment occurs in a third subject in a dose group, the fifth subject may be enrolled. Finally, when engraftment occurs in a fourth subject in a dose group, the sixth subject may be enrolled.

After all subjects in a dose group have completed study procedures through Day 28, all available safety information will be reviewed by the DSMB. Dosing may begin for the next dose group at the next higher dose level if no more than one subject in the previous group has experienced a DLT and, in the opinion of the DSMB, there are no clinically significant safety concerns at the previous dose level. If, in the opinion of the DSMB, there are clinically significant safety concerns, the DSMB may recommend that the study be discontinued.

If graft failure occurs in any dose group, that dose group will be expanded to 12 subjects. If a second graft failure occurs in the expanded cohort, the DSMB will determine if the study should be stopped after looking at the data for the two subjects whose grafts failed. As with other dose groups, enrollment in the expanded cohort will be staggered to minimize the chance of multiple graft failures. Only two subjects may be simultaneously enrolled until one of them successfully engrafts, at which time an additional subject may be enrolled.

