4.3 Study Assessments

Study assessments are shown in the Schedule of Assessments (Appendix 1). Routine laboratory analyses, including chemistries, CBC, coagulation measures, and urinalysis will be performed locally at the study sites. Surface markers requiring same day analysis (e.g., TLR4) will also be processed and analyzed locally, though in some circumstances these samples may be frozen, batched and sent to a central lab. All other samples will be analyzed at a central lab.

The following assessments will be performed daily from Day –1 until Day 49 or until the subject is released from the hospital, whichever occurs first:

- Metabolic assessment (Intake and output [I&O] and total days of parenteral nutrition [TPN] only). Assessments requiring daily totals should be measured by calendar day (i.e., from midnight to midnight) unless otherwise specified by institutional standard practice.
- Vital signs including pulse, blood pressure (systolic/diastolic), respiratory rate, and temperature taken in the morning (i.e., the first waking set of vital signs). If a subject experiences an SAE, vital signs must be taken more frequently, per standard institutional practice.

In addition, the oral mucositis score must be recorded at prescreening and then daily from Day –1 through Day 7 (see Appendix 5 for grading scale). After Day 7, the oral mucositis score must be recorded daily until the condition resolves to grade 0. If oral mucositis reappears after resolving, daily assessments must be reinstituted through Day 49 or until the subject is released from the hospital, whichever occurs first.

All assessments scheduled on Days 14, 21, and 28 must be performed for all subjects whether or not the subjects have been discharged from the hospital. Assessments scheduled on Days 35, 42 and 49 will be performed only for those subjects who are still hospitalized on those days. Note that assessments scheduled between Day 14 and Day 49 (excluding Days 21, 28, 35, and 42) are not shown in the table for Appendix 1 (Study BPSC030 Schedule of Assessments), though they are mentioned in the footnotes for the assessments that are affected (i.e., Footnote 14 [metabolic assessment], Footnote 15 [vital signs], and Footnote 21 [oral mucositis]).

Several of the assessments performed during this study are considered "over and above" those normally performed as part of routine patient care for HSCT procedures. These special assessments are as follows:

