Appendix 1 (continued) Footnotes to Study BPSC030 Schedule of Assessments

- Assessments performed on consenting donors must be performed prior to stem cell harvest.
- Prescreening assessments must take place within 30 days of admission to the hospital for the conditioning regimen and subsequent HSCT procedure.
- Final screening must take place within 12 hours prior to the initiation of treatment with opebacan. Prior to opebacan administration, the Principal Investigator or designee must review and approve subject eligibility and must confirm that the interval between initiating opebacan and administering donor cells will be between 18 and 36 hours.
- The HSCT procedure must be performed no less than 18 hours and no more than 36 hours after completion of chemotherapy treatment. Subjects whose conditioning regimen consists of chemotherapy only will receive a continuous opebacan infusion following completion of chemotherapy treatment on Day –1. Subjects whose conditioning regimen includes TBI will have three 1-hour interruptions in their opebacan infusions (one on Day –1 and two on Day 0) to accommodate TBI treatment. Following the final interruption on Day 0, the infusion must be restarted at least 2 hours prior to the HSCT.
- All assessments scheduled on Days 14, 21, and 28 must be completed for all subjects whether or not the subjects have been discharged from the hospital. Assessments scheduled on Days 35, 42 and 49 will be performed only for those subjects who are still hospitalized on those days. Note that assessments taking place between Day 14 and Day 49 (excluding Days 21, 28, 35, and 42) are not shown in the Schedule of Assessments, though they are mentioned in the footnotes for the assessments for the metabolic assessment (Footnote 14), vital signs (Footnote 15), and oral mucositis score (Footnote 21).
- The assessments marked for Day 100/aGvHD should be performed at the Day 100 (± 14 day) final follow-up visit and whenever a subject is diagnosed with ≥ grade 2 aGvHD (see Appendix 4 for Consensus Grading Scale). The Day 100 visit should be performed in the clinic, if possible. If this is not possible, study personnel should call the subject or subject's attending physician to obtain as much of the Day 100 assessment information as possible.
- Demographics and medical history, including virology and serology status taken at prescreen; interim medical history taken at final screen and predose.

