- BPI and defensin content of patient-derived neutrophil extracts similar to that of normal controls
- BPI range is quite broad
- Severe neutropenia likely renders host deficient in total body content of antimicrobial proteins/peptides

[figure not shown]
Endotoxemia and elevation of lipopolysaccharide-binding protein after hematopoietic stem cell transplantation

[name], PHD, ARMANDO TEIXEIRA-PINTO, MS, MARK L. WHITE, BS, STEPHEN F. CARROLL, PHD, [name], DAVID WYPIJ, PHD AND [name]

THE PEDIATRIC INFECTIOUS DISEASE JOURNAL

Vol. 22, No. 11, Nov. 2003

• 11/25 (44%) patients had endotoxemia at somepoint after HSCT

CRP & LBP elevated at Day 7 and correlated with one another

Tumor Necrosis Factor– α Production to Lipopolysaccharide Stimulation by Donor Cells Predicts the Severity of Experimental Acute Graft-Versus-Host Disease

Kenneth R. Cooke,* Geoffrey R. Hill,* James M. Crawford,[‡] David Bungard,* Yani S. Brinson,* John Delmonte, Jr.,* and James L.M. Ferrara*

*Department of Pediatric Oncology Dana-Farber Cancer Institute, Children's Hospital, and Harvard Medical School, Boston, Massachusetts 02115 and the [‡]Department of Pathology, Yale University School of Medicine, New Haven, Connecticut 06520-8023

J. Clin. Invest.

© The American Society for Clinical Investigation, Inc. 0021-9738/98/11/1882/10 \$2.00

Volume 102, Number 10, November 1998, 1882–1891

- Murine GVHD model
- LPS-induced TNF-α predicts aGVHD
- Mice with hypomorphic mutations in TLR4 (part of LPS receptor complex) do not get aGVHD
- Interpretation of murine model: LPS translocates from gut to systemic circulation and triggers, via TLR4, TNF- α that results in aGVHD

Do endotoxemia and endotoxin-directed innate immunity play a role in human aGVHD?

rBPI₂₁ to Prevent aGVHD: Hypothesis

- Myeloablative conditioning regimens followed by HSCT will induce innate immune responses triggered in part by endotoxemia
- Endotoxemia is contributory/necessary (but not sufficient) for subsequent aGVHD
- Neutropenia is associated with low BPI levels
- Prior to engraftment, the BPI/LBP ratio will be low
- If the above is correct, then IV infusion of rBPI₂₁ early during HSCT may modulate subsequent aGVHD

Natural History Study Design

[figure not shown]
Measure endotoxin and endotoxin-directed proteins of the innate immune system in patients undergoing HSCT

[figure not shown]
- Peripheral blood collected from donors and from pediatric and adult patients undergoing sibling HSCT

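### Section 6.4 summarises levels and markers only within dose groups of about six, by arithmetic mean, although early exposure is shared across groups and the Day 35 markers come from inpatients only

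*Supplement*

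**What the plan says.** Section 6.4 sets the summary for markers and drug levels: "The mean of inflammatory markers (e.g., LPS and LBP) and opebacan plasma levels will be summarized by assessment time point and dose group". It also correlates fever and infection with LPS and LBP within each dose group. Section 6.2 gives the group size: "The planned accrual is six subjects in each of the five successive dose groups". Section 3.3.4 allows an exception: "If graft failure occurs in any dose group, that dose group will be expanded to 12 subjects".

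Table 1 gives the Group 4 regimen as "4 mg/kg continuous IV infusion for 30 minutes followed immediately by 12 mg/kg/day continuous IV infusion for 7 days". Groups 3 and 5 have the same load and the same daily rate, for 3 and 14 days. Appendix 2 gives all five groups the same PK times up to 2880 minutes after the start of infusion.

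On late visits, Section 4.3 says: "Assessments scheduled on Days 35, 42 and 49 will be performed only for those subjects who are still hospitalized on those days". Assessments on Days 14, 21 and 28 are for everyone. Section 6.6 rules out imputation. Appendix 1, footnote 6, applies the Day 100 set of assessments also "whenever a subject is diagnosed with ≥ grade 2 aGvHD".

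Two related passages matter. Section 6.5.2 adds changes from baseline in the same markers, again by dose group. Section 6.0 limits the study to descriptive statistics without formal testing.

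**The concern.** Objective 2 is pharmacokinetics and Objective 3 is change in inflammatory markers. For the 30-minute peak, dose group carries no information about planned exposure, because every subject has had the same load. For levels up to 48 hours, Groups 3, 4 and 5 are on the same regimen. A table that shows only sixes reports several imprecise estimates of one quantity and never the better one.

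Three further features make the planned summaries hard to read:

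- **Scale.** Section 3.2.1.1 says endotoxin enters the blood erratically and gives erratic levels. The slides after Appendix 5 report that "11/25 (44%) patients had endotoxemia at somepoint after HSCT". In six subjects, an arithmetic mean of such a marker can be set by one person.
- **Day 35.** LPS, LBP, soluble and surface markers are scheduled then, but only in subjects still in hospital. The population behind the mean changes between Day 28 and Day 35, and Section 6.4 has no rule for this.
- **Day 100 column.** Scheduled draws and draws prompted by an aGvHD diagnosis sit under one heading in Appendix 1.

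**Working it through.** **1. Planned exposure.** Table 1 totals follow from 4 + rate × days: 4 + 6×3 = 22, 4 + 9×3 = 31, 4 + 12×3 = 40, 4 + 12×7 = 88 and 4 + 12×14 = 172 mg/kg. All five agree with the table. Nominal dose by 48 hours is 4 + 6×2 = 16 in Group 1, 4 + 9×2 = 22 in Group 2, and 4 + 12×2 = 28 mg/kg in each of Groups 3, 4 and 5. The interruptions for total body irradiation apply in any group, so they do not separate these three.

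**2. Which samples are shared.** PK: 30, 45, 90, 270, 1440 and 2880 minutes in Groups 3–5, and the 30-minute sample in all groups. Inflammatory markers: predose and Day 0 only. Appendix 1 has no marker draw on Day 1. The Day 2 draw follows the end of infusion in Group 3 but falls during infusion in Groups 4 and 5.

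**3. Precision.** The plan gives no CV and no sample-size calculation, so CV is an assumption. For log-normal data the 95% factor is exp(t(0.975, n−1) × s/√n), with s = √ln(1 + CV²). At CV 40%, s = √ln 1.16 = 0.385.

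| n | t | t/√n | Factor, CV 40% | CV 30% to 60% |
|---|---|---|---|---|
| 6 | 2.571 | 1.049 | 1.50 | 1.36 to 1.79 |
| 18 | 2.110 | 0.497 | 1.21 | 1.16 to 1.32 |
| 30 | 2.045 | 0.373 | 1.15 | 1.12 to 1.23 |

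With 12 subjects (one expanded group, or Groups 3 and 4 alone if escalation stops there), t = 2.201 and the factor at 40% is exp(2.201 × 0.385/√12) = 1.28.

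**4. Correlations.** Take r = 0.5 for illustration, Fisher z = 0.549, SE = 1/√(n−3). With n = 6: 0.549 ± 1.96×0.577, giving −0.52 to 0.93. With n = 30: 0.549 ± 1.96×0.192, giving 0.17 to 0.73. Allowing for dose as one covariate replaces n−3 by n−4 = 26 and gives 0.16 to 0.73.

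**5. Scale.** For a log-normal marker, arithmetic mean/geometric mean = √(1 + CV²): 1.08 at CV 40%, 1.41 at 100%, 2.24 at 200%. By simulation, one of six subjects supplies more than half the sum in 13% of groups at CV 100% and 39% at 200%. These CVs are assumed.

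**6. Day 35.** If a share q is still in hospital (assumed), a group of six yields 6q values on average, and the chance of at most one is (1−q)⁶ + 6q(1−q)⁵.

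| q | Expected values | P(at most one) |
|---|---|---|
| 10% | 0.6 | 0.89 |
| 20% | 1.2 | 0.66 |
| 30% | 1.8 | 0.42 |
| 50% | 3.0 | 0.11 |

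**The case against.** The strongest reply is that the study is descriptive, no analysis plan is shown, and pooling, labelling and detection-limit rules are commonly left to that plan. Pooling also remains possible later from the same data. This is fair as to detail. But Section 6.4 does name a method (the mean, and correlations, by dose group), and that method is weaker than alternatives that cost almost nothing.

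Several other points stand and limit the concern:

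- By-group PK is needed: Section 6.8 uses PK data for escalation, and the groups are sequential and not randomised.
- Pooling adds little for Objective 3. Day 0 is the only clean shared post-dose marker time, 1 of 11 scheduled for LPS and LBP (Days 0, 2, 4, 6, 8, 10, 14, 21, 28, 35 and 100).
- The skew argument concerns LPS. Section 1.4 reports nearly universal LBP elevation by Day 7, and at CV 40% the two means differ by only 8%.
- The Fisher interval assumes one continuous pair per subject. Fever and infection are states and markers are repeated, so it shows scale only.
- Section 6.5.2 plans changes from baseline. Section 3.1 plans exploratory PK correlations without a by-group limit, and Section 6.7 does not tie the peak to dose groups.

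A reader might infer that Day 35 will show a false late rise in inflammation. The documents give neither the inpatient share nor marker values, so distortion is possible but not shown. Nor do they say that triggered draws will be averaged with Day 100; the two share a column.

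A reader might also infer that aGvHD grading between Days 28 and 56 depends on hospital stay, since Section 3.2.1.2 says "onset of aGvHD in humans starts between post-transplant Days 21 and 42" and Day 42 grading is for inpatients. Only that scheduled grading does. Footnote 6 covers grade 2 or higher in outpatients, GvHD is collected as an adverse event, and cumulative status is confirmed in all subjects at Day 100. What is exposed is mainly grade I disease and timing. Phone grading would not mend this, because Appendix 4 staging needs bilirubin, stool volume and rash area.

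**Conclusion.** The point holds as a weakness of precision and interpretation; no figure in the plan is wrong. The largest gain is for the 30-minute peak, where the 95% factor at CV 40% falls from 1.50 (n = 6) to 1.15 (n = 30). For Groups 3–5 levels up to 48 hours it falls to 1.21 (n = 18). These sizes rest on an assumed CV, on log-normal data, on all groups being filled as planned, and on no drift between sequential cohorts. Correlations within groups of six are close to uninformative. The case against arithmetic means is firm for LPS and weaker for other markers. Day 35 is the only marker visit limited to inpatients (Days 42 and 49 have no inflammatory markers). It should not be read as part of the same time course as Days 14 to 28.

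**What to change.** 1. Keep the by-group tables and add, beside them, the 30-minute peak pooled over all subjects, PK levels through 48 hours pooled over Groups 3–5, and markers pooled over Groups 3–5 at predose and Day 0 only.
2. Run the correlations of markers with fever and infection over all subjects, allowing for dose and for repeated measures within subject.
3. Replace the mean by the median with interquartile range or the geometric mean, and report the percentage detectable for LPS.
4. Label Day 35 markers as inpatients only, show the number contributing, and leave them out of time-course plots. Give aGvHD-triggered draws their own time point, apart from Day 100.

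The cost is revised wording in Section 6.4 or the analysis plan and a few table shells. No visit, sample or subject is added.
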